
• Estimate the durability of efficacy up to 5 years after PF-07055480 infusion.	
The following parameters will be analyzed yearly or by visit as appropriate:
 
• ABR.• FVIII activity level.• AIR of exogenous FVIII.• Annualized FVIII consumption.• ABR of specific type:
○ by cause (spontaneous or traumatic).○ by location (in joint, in target joints, or in soft tissue).• Total ABR.• Total ABR by cause and by location.• Percentage of participants without bleeds.• Change from baseline in joint health as measured by the HJHS instrument.• Change from baseline in PRO endpoints: Haem-A-QoL and HAL. 
In addition, ABR, Total ABR, and AIR will be analyzed throughout the 5-year study period.

Secondary Safety Objective	Secondary Safety Endpoints

• To estimate the safety and tolerability of PF-07055480, including immunogenicity, for the study duration of 5 years after PF-07055480 infusion.	
• Incidence and severity of AEs.• Events of special interest (such as hypersensitivity reactions, clinically

Objectives	Endpoints
	
reported thrombotic events, and malignancy).
 
 • Immunogenicity: 
 ○ Antibodies against AAV6 capsid protein (nAbs and ADAs). ○ T-cell responses against AAV6 capsid and against the transgene. ○ FVIII inhibitors.
Tertiary/Exploratory	

 • To evaluate vector shedding and infectivity in body fluids. 	
 • Vector shedding and infectivity of PF-07055480 in plasma, saliva, PBMC, urine, and semen until negative on 3 consecutive occasions for each specimen type.

 • To evaluate exploratory pharmacodynamic biomarkers. 	
 • FVIII antigen levels. • Von Willebrand factor.

 • To compare joint health post PF-07055480 infusion to baseline and evaluate long-term joint outcomes. 	
 • Number of target joints. • Joint status as assessed by X-ray. • Joint status as assessed by ultrasound.

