- The investigator will then record all relevant AE/SAE information in the CRF.
- It is **not** acceptable for the investigator to send photocopies of the participant's medical records to Pfizer Safety in lieu of completion of the CT SAE Report Form/AE/SAE CRF page.
- There may be instances when copies of medical records for certain cases are requested by Pfizer Safety. In this case, all participant identifiers, with the exception of the participant number, will be redacted on the copies of the medical records before submission to Pfizer Safety.
- The investigator will attempt to establish a diagnosis of the event based on signs, symptoms, and/or other clinical information. Whenever possible, the diagnosis (not the individual signs/symptoms) will be documented as the AE/SAE.

Assessment of Intensity

The investigator will make an assessment of intensity for each AE and SAE reported during the study and assign it to 1 of the following categories:
 
 • Mild: An event that is easily tolerated by the participant, causing minimal discomfort and not interfering with everyday activities. • Moderate: An event that causes sufficient discomfort and interferes with normal everyday activities. • Severe: An event that prevents normal everyday activities. An AE that is assessed as severe should not be confused with a SAE. Severe is a category utilized for rating the intensity of an event; and both AEs and SAEs can be assessed as severe. 
An event is defined as ‘serious’ when it meets at least 1 of the predefined outcomes as described in the definition of an SAE, NOT when it is rated as severe.

Assessment of Causality

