10.6. Appendix 6: Liver Safety: Suggested Actions and Follow-up Assessments

Humans exposed to a drug who show no sign of liver injury (as determined by elevations in transaminases) are termed “tolerators,” while those who show transient liver injury, but adapt are termed “adaptors.” In some participants, transaminase elevations are a harbinger of a more serious potential outcome. These participants fail to adapt and therefore are “susceptible” to progressive and serious liver injury, commonly referred to as DILI. Participants who experience a transaminase elevation above 3 times the upper limit of normal (\times ULN) should be monitored more frequently to determine if they are an “adaptor” or are “susceptible.”

In the majority of DILI cases, elevations in AST and/or ALT precede TBili elevations ($>2 \times$ ULN) by several days or weeks. The increase in TBili typically occurs while AST/ALT is/are still elevated above $3 \times$ ULN (ie, AST/ALT and TBili values will be elevated within the same lab sample). In rare instances, by the time TBili elevations are detected, AST/ALT values might have decreased. This occurrence is still regarded as a potential DILI. Therefore, abnormal elevations in either AST OR ALT in addition to TBili that meet the criteria outlined below are considered potential DILI (assessed per Hy’s law criteria) cases and should always be considered important medical events, even before all other possible causes of liver injury have been excluded.

The threshold of laboratory abnormalities for a potential DILI case depends on the participant’s individual baseline values and underlying conditions. Participants who present with the following laboratory abnormalities should be evaluated further as potential DILI (Hy’s law) cases to definitively determine the etiology of the abnormal laboratory values:

- Participants with AST/ALT and TBili baseline values within the normal range who subsequently present with AST OR ALT values $>3 \times$ ULN AND a TBili value $>2 \times$ ULN with no evidence of hemolysis and an alkaline phosphatase value $<2 \times$ ULN or not available;
- For participants with baseline AST OR ALT OR TBili values above the ULN, the following threshold values are used in the definition mentioned above, as needed, depending on which values are above the ULN at baseline:

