A potential DILI (Hy's law) case becomes a confirmed case only after all results of reasonable investigations have been received and have excluded an alternative etiology.

Unique to PF-07055480 is the potential for T-cell induced hepatocyte destruction. In some cases, presentation of AAV capsid protein by MHC to the surface of a hepatocyte can trigger CD8 cell mediated targeting of hepatocytes. This presents asymptotically with a rise in LFTs and/or a decline in FVIII activity levels. This effect is not due to direct hepatocyte toxicity rather it is an immunologic response. This immunologic reaction has been shown in prior studies and more particularly in 2 participants in the Phase 1/2a dose escalation study who have both responded to a short course of corticosteroids.

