6.6.1. Adverse Events

The AE data will be summarized following the latest available version of MedDRA.

An overall table summarizing TEAEs reported during the entire study will be sorted by System Organ Class (SOC) and Preferred Term (PT). Per protocol, adverse events assessed as non-serious and unrelated to study drug are reported within the first two years postinfusion only and are not subject to reporting thereafter. Therefore, the all causality TEAE tables will include a footnote to convey non-serious unrelated AEs were collected over the first two years and not the subsequent 3-year study duration for a given participant.

All TEAEs occurring during the short-term monitoring period (up to and including 104 weeks postinfusion) will be summarized, sorted by SOC and PT. All AE summary tables

will be generated to display all AEs, relationship to study drug, and severity of the AEs ('Mild', 'Moderate', and 'Severe').

All serious AEs, treatment-related non-serious AEs, events of special interest, AEs related to corticosteroid treatment as deemed by the investigator, AEs leading to study discontinuation, and AEs leading to death will be summarized for adverse events reported during the short-term monitoring period (up to and including 104 weeks postinfusion) and AEs reported during the long-term monitoring (Week 105 post PF-07055480 infusion up to EOS), respectively if data are available.

TEAEs and SAEs will be summarized separately for the 'Safety' population.

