6.6.2. Laboratory Data

Data of safety laboratory tests and other laboratory tests collected at scheduled study visits will be summarized according to the data type. Data collected at both scheduled visit and unscheduled visits will be included in plots.

Any important laboratory abnormality identified will be summarized as described below.

Categorical shift of abnormal to normal, or normal to abnormal, in liver function test (LFT), α -Fetoprotein (AFP), hematology, and clinical chemistry parameters will be summarized.

Laboratory tests included in LFT measures are listed in the Protocol Appendix 2. Baseline and post baseline observations will be summarized with descriptive statistics by visit and will be presented in a data listing. Number of participants (n), mean, SD, median, Q1, Q3, min and max will be presented for all change from baseline tables. Individual laboratory values will be classified according to whether the test result is 'low' (i.e., below the lower limit of normal), 'normal' (i.e., within the normal range), or 'high' (i.e., above the upper limit of normal). The abnormality categorical data will be summarized in shift tables comparing the results at the end of study visit, minimum post-baseline, and maximum post-baseline with those at the baseline visit.

The following laboratory tests presented in [Table 9](#) will be reported in shift tables.

Table 9. Laboratory Tests to be Presented in Shift Tables

Hemoglobin
Hematocrit
Selected LFTs, including albumin, alanine transaminase (ALT), aspartate transaminase (AST), bilirubin (total, direct), alkaline phosphatase (ALP), gamma-glutamyl transferase (GGT), lactic acid dehydrogenase (LDH)
AFP
aPTT (in ratio), INR, TAT, TGA, D-dimer
White blood cell (WBC) count total
Neutrophils
Lymphocytes
Monocytes
Eosinophils
Basophils
Serum creatinine

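### No planned safety summary separates a small from a large symptom-free ALT/AST rise, or gives a labelled count against the Appendix 6 liver criteria

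*Protocol*

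**What the plan says.** **Intensity.** Under Protocol 10.3.3 the investigator gives each AE one of three levels. The lowest is defined as "Mild: An event that is easily tolerated by the participant, causing minimal discomfort and not interfering with everyday activities". The middle level needs enough discomfort to disturb daily life, and the highest is defined as "Severe: An event that prevents normal everyday activities". The section keeps seriousness separate from intensity. SAP 6.6.1 displays AE severity on these three levels.

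**Laboratory values.** SAP 6.6.2 has three classes, low, normal and high, where high means anything above the ULN; the rule opens with "Individual laboratory values will be classified according to whether the test result is". Shift tables set the baseline category against the category at end of study and at the post-baseline minimum and maximum. The section also plans by-visit descriptive statistics, change from baseline with minimum and maximum, a data listing, and an ALT/AST plot for every participant in the Safety population. Laboratory summaries draw on scheduled visits; unscheduled values are mentioned for plots only.

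**Liver rules.** Protocol Appendix 6 (10.6) asks for closer monitoring above 3 × ULN and then says: "Participants who present with the following laboratory abnormalities should be evaluated further as potential DILI". With normal baseline values the criteria are ALT or AST above 3 × ULN together with total bilirubin above 2 × ULN, no evidence of hemolysis, and ALP below 2 × ULN or not available. Separate thresholds apply when a baseline value is already raised. Of the vector-related immune reaction the appendix says: "This presents asymptotically with a rise in LFTs and/or a decline in FVIII activity levels". I read the adverb as a slip for asymptomatically.

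**Endpoint.** "Incidence and severity of AEs" is a secondary safety endpoint (Protocol section 3), and hepatotoxicity is the first of the main potential risks listed in the synopsis.

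**The concern.** The protocol expects the immune liver reaction to show mainly in laboratory values, and Appendix 6 treats the height of the rise as what matters. The two categorical scales planned for reporting both ignore height. A participant without symptoms fits only the mild definition whatever the ALT, and every value above the ULN is high.

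Such rises do reach the AE data. Protocol 10.3.1 requires an abnormal result to be recorded as an AE when it needs medical intervention or leads to significant additional drug treatment, and section 8.3.10 has corticosteroids considered at modest ALT increases. At stake is whether the planned tables for a secondary safety endpoint describe how large the liver reactions were.

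**Working it through.** No design figure (power, alpha, margin) is involved, so the check passes assumed ALT values through the two written rules.

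**Inputs**
- SAP 6.6.2: high = above 1 × ULN, with no upper cut.
- Appendix 6, ALT part, normal baseline: above 3 × ULN.
- Appendix 6, ALT part, raised baseline b: above 2b and above 3 × ULN, or above 8 × ULN, whichever is smaller. In multiples of ULN the threshold is min(max(2b, 3), 8).
- Protocol 5.2, exclusion criterion 6: ALT above 2 × ULN is excluded, so a baseline between 1 and 2 × ULN is allowed and already counts as high.

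**Thresholds**
- b = 0.6 (normal): 3.
- b = 1.8: min(max(3.6, 3), 8) = 3.6.
- b = 2.0, the eligibility limit: min(max(4.0, 3), 8) = 4.0.
- The 8 × ULN alternative would be the smaller one only if 2b > 8, that is b > 4, twice the eligibility limit.

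**Result (baselines and peaks are assumed, × ULN)**

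| Baseline | Peak | SAP shift cell (maximum) | ALT part of Appendix 6 |
|---|---|---|---|
| 0.6 | 1.1, 2.0 | normal to high | not met |
| 0.6 | 3.1, 5.1, 8.1, 20.1 | normal to high | met (above 3) |
| 1.8 | 1.1, 2.0, 3.1 | high to high | not met |
| 1.8 | 5.1, 8.1, 20.1 | high to high | met (above 3.6) |

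All six peaks share one cell at each baseline. From 1.8 × ULN even a peak of 20.1 × ULN registers no shift. The Appendix 6 rule does separate them, but no planned table uses it.

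**The other planned outputs**
- By-visit maxima give one value per visit, not a number of participants above a threshold.
- The listing and plots hold the values, but counting from them is not planned.
- Summaries rest on scheduled visits. Under section 8.3.10, at least two LFT draws a week are recommended while corticosteroids are given, so a peak may be found outside the visit schedule and miss the tables.
- SAP 6.5.4 counts corticosteroid use, escalations and courses. That describes treatment, not the height of the rise.

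**The case against.** The strongest reply is that the worst liver cases do not depend on either scale. Appendix 6 makes potential Hy's law cases SAEs before the work-up is complete. Protocol 10.3.2 makes drug-related elevations that fail to improve on immunosuppression medically important events, hence SAEs, and section 8.3.8 makes those events of special interest. SAP 6.6.1 summarises both groups. All ALT and AST values are listed and plotted, safety analyses are descriptive, and no test or endpoint definition changes. On this view an extra table is a matter of presentation.

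Most of this stands, and it rules out several stronger readings:
- A reader might infer that liver injury is never graded, or that the trial could not say how many participants passed 3 × ULN. The values are in the database and the two SAE routes exist. What is missing is a planned count.
- A reader might take hepatotoxicity to be the single main risk. It is one of four listed.
- A reader might assume that every ALT rise becomes a mild AE. Only clinically significant results, or those meeting the conditions in 10.3.1, are recorded, and the investigator assigns the level.
- A reader might treat 8 × ULN as a general Appendix 6 cut-point. It applies only to raised baselines and does not come into play at an eligible baseline.

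The reply leaves one case open: a large isolated ALT rise that settles on corticosteroids meets neither SAE route through those rules. Protocol 2.3.1 suggests this is the expected case, since it reports that all transitory LFT elevations in the Phase 1/2 study were treated successfully with corticosteroids. Even the SAE routes give no labelled Hy's law count, and an SAE can still carry mild intensity.

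**Conclusion.** The point holds as a reporting gap, not a loss of data. No planned summary separates small from large symptom-free ALT/AST rises, and none gives a labelled count against the Appendix 6 criteria. Its size is structural: peaks from just above 1 × ULN upward share one laboratory category, and symptom-free events share one intensity level. The documents give no rate of high elevations, so the number of participants affected cannot be stated.

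The conclusion assumes that the adverb in Appendix 6 means without symptoms, that investigators apply the intensity definitions as written, and that the scheduled-visit rule in SAP 6.6.2 also governs the shift tables, which the SAP does not say explicitly. The last assumption affects only whether off-schedule peaks are missed; the single high category remains either way. This is an inexpensive improvement worth making before the analysis.

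**What to change.** **SAP 6.6.2**
- Add a table of worst post-baseline ALT, AST and total bilirubin, using scheduled and unscheduled values, that splits high at the Appendix 6 thresholds: above 3 × ULN for ALT/AST and above 2 × ULN for bilirubin.
- Label any further bands as display categories, not as Appendix 6 cut-points.
- For participants with a raised baseline, show multiples of baseline or change from baseline under the baseline-adjusted Appendix 6 criteria, including those for bilirubin.
- Add the number of participants meeting the full potential Hy's law criteria.

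**SAP 6.6.1**
- For transaminase AEs, show peak ALT/AST as a multiple of ULN beside the investigator's intensity level.

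The cost is SAP wording and one or two tables from data already collected. Participant management does not change. The downside is a liver safety summary that may look less favourable.

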10.3.4. Reporting of SAEs

SAE Reporting to Pfizer Safety via an Electronic Data Collection Tool

- The primary mechanism for reporting an SAE to Pfizer Safety will be the electronic data collection tool.
- If the electronic system is unavailable, then the site will use the paper SAE data collection tool (see next section) in order to report the event within 24 hours.
- The site will enter the SAE data into the electronic system as soon as it becomes available.
- After the study is completed at a given site, the electronic data collection tool will be taken off-line to prevent the entry of new data or changes to existing data.
- If a site receives a report of a new SAE from a study participant or receives updated data on a previously reported SAE after the electronic data collection tool has been taken off-line, then the site can report this information on a paper SAE form (see next section) or to the Pfizer Safety by telephone.
- Contacts for SAE reporting can be found in the ISF.

SAE Reporting to Pfizer Safety via Paper CRF

- Facsimile transmission of the SAE paper CRF is the preferred method to transmit this information to Pfizer Safety.
- In rare circumstances and in the absence of facsimile equipment, notification by telephone is acceptable with a copy of the SAE data collection tool sent by overnight mail or courier service.
- Initial notification via telephone does not replace the need for the investigator to complete and sign the SAE CRF pages within the designated reporting time frames.
- Contacts for SAE reporting can be found in the ISF.

10.4. Appendix 4: Contraceptive Guidance and Collection of Pregnancy Information

Contraception Guidance:

Contraception guidance for the male participants until at least 3 consecutive ejaculate samples test negative for vector shedding as follows:

- Refrain from donating sperm

PLUS either:

- Be abstinent from heterosexual or homosexual intercourse as their preferred and usual lifestyle (abstinent on a long term and persistent basis) and agree to remain abstinent.

OR

- Must agree to use contraception/barrier as detailed below.
 - Agree to use male condom when engaging in any activity that allows for passage of ejaculate to another person.

Collection of Pregnancy Information:

For both unapproved/unlicensed products and for marketed products, an EDP occurs if:

- A female becomes, or is found to be, pregnant either while receiving or having been exposed (eg, because of treatment or environmental exposure) to the investigational product; or the female becomes or is found to be pregnant after discontinuing and/or being exposed to the investigational product;
 - An example of environmental exposure would be a case involving direct contact with a Pfizer product in a pregnant woman (eg, a nurse reports that she is pregnant and has been exposed to chemotherapeutic products).
- A male has been exposed (eg, because of treatment or environmental exposure) to the investigational product prior to or around the time of conception and/or is exposed during his partner's pregnancy.

If a participant or participant's partner becomes or is found to be pregnant during the participant's treatment with the investigational product, the investigator must report this information to Pfizer Safety on the CT SAE Report Form and an EDP supplemental form, regardless of whether an SAE has occurred. In addition, the investigator must submit information regarding environmental exposure to a Pfizer product in a pregnant woman (eg, a participant reports that she is pregnant and has been exposed to a cytotoxic product by inhalation or spillage) to Pfizer Safety using the EDP supplemental form. This must be done irrespective of whether an AE has occurred and within 24 hours of awareness of the exposure. The information submitted should include the anticipated date of delivery (see below for information related to termination of pregnancy).

Follow-up is conducted to obtain general information on the pregnancy and its outcome for all EDP reports with an unknown outcome. The investigator will follow the pregnancy until completion (or until pregnancy termination) and notify Pfizer Safety of the outcome as a follow-up to the initial EDP supplemental form. In the case of a live birth, the structural integrity of the neonate can be assessed at the time of birth. In the event of a termination, the reason(s) for termination should be specified and, if clinically possible, the structural integrity of the terminated fetus should be assessed by gross visual inspection (unless pre-procedure test findings are conclusive for a congenital anomaly and the findings are reported).

If the outcome of the pregnancy meets the criteria for an SAE (ie, ectopic pregnancy, spontaneous abortion, intrauterine fetal demise, neonatal death, or congenital anomaly [in a live-born baby, a terminated fetus, an intrauterine fetal demise, or a neonatal death]), the investigator should follow the procedures for reporting SAEs.

Additional information about pregnancy outcomes that are reported to Pfizer Safety as SAEs follows:

- Spontaneous abortion includes miscarriage and missed abortion;
- Neonatal deaths that occur within 1 month of birth should be reported, without regard to causality, as SAEs. In addition, infant deaths after 1 month should be reported as SAEs when the investigator assesses the infant death as related or possibly related to exposure to the investigational product.

Additional information regarding the EDP may be requested by the sponsor. Further follow-up of birth outcomes will be handled on a case-by-case basis (eg, follow-up on preterm infants to identify developmental delays). In the case of paternal exposure, the investigator will provide the participant with the Pregnant Partner Release of Information Form to deliver to his partner. The investigator must document in the source documents that the participant was given the Pregnant Partner Release of Information Form to provide to his partner.

